There are currently no licensed treatments for chronic pouchitis and the current treatment is largely empiric or guided by low-quality evidence from case series and small observational studies. Chronic antibiotic therapy is a potential treatment option only for patients with chronic antibiotic dependent pouchitis (CADP) though it is associated with risk of antibiotic related side effects and emergence of multi-drug resistant organisms^{7,8}. Other commonly used treatments for chronic pouchitis are ileal release budesonide and biologic drugs. Ileal release budesonide is effective in 58-75% patients with chronic pouchitis but its chronic use is associated with long-term corticosteroid-associated side effects and is generally discouraged^{9,10}. Anti-tumor necrosis factor (anti-TNF) agents are widely used for treatment of chronic pouchitis though a recent meta-analysis found these medications to be only modestly effective with remission rates of 10% and 37% in short-term and long-term, respectively, in patients with chronic antibiotic-refractory pouchitis (CARP)¹¹. A few recent observational studies suggest that vedolizumab and ustekinumab could also be effective in chronic pouchitis but the remission rates with these drugs also remain low^{12,13}. Hence, given the availability of limited treatment options in chronic pouchitis and their modest efficacy, there is a significant unmet need for additional effective medical therapies in these patients. This treatment gap is likely to worsen in the future as the population of patients who undergo IPAA surgery for UC increases with time.

Janus kinases (JAKs) play a central role in transmitting the pro-inflammatory effects of multiple cytokines that result in chronic inflammation in inflammatory bowel diseases¹⁴. Targeting the JAK-STAT pathway is an effective therapeutic approach in inflammatory bowel diseases (IBD). Tofacitinib, an oral small molecule JAK inhibitor is effective and safe for treatment of ulcerative colitis¹⁵. JAK-STAT pathway might also have a potential role in the pathogenesis of chronic pouchitis. In a study of thirty-six patients who underwent IPAA surgery for UC, patients who

develop pouchitis were noted to have increased levels of STAT1alpha as well as STAT1beta expression and activation in comparison with both normal pouch and normal ileal mucosa. In addition, improvement of pouchitis after treatment with antibiotics was associated with normalization of STAT1 expression and activation¹⁶. These findings suggest that activation of STAT1 correlates with pouchitis disease activity. Currently, there is no data on the efficacy of JAK inhibitors in treatment of chronic pouchitis. However, similarities in the pattern of activation of STAT1 in pouchitis and ulcerative colitis may suggest a common pathway in the immunobiology of both diseases and a potential role for JAK inhibitors like tofacitinib in treatment of chronic pouchitis.

Aims and Objectives

This study is designed to evaluate the efficacy and safety of oral tofacitinib in subjects with chronic pouchitis and its impact in health-related quality of life. Chronic pouchitis is defined by a modified pouchitis disease activity index (mPDAI) score ≥ 5 and a minimum endoscopic subscore of 2 (outside the staple or suture line) AND one of the following:

- ≥ 3 recurrent episodes of pouchitis within 1 year prior to the screening visit treated with ≥ 2 weeks of antibiotic or other prescription therapy.
- Requiring maintenance antibiotic therapy taken continuously for ≥ 4 weeks immediately prior to the baseline study visit.
- No response to $>= 4$ weeks of antibiotic therapy.

Objective 1: Assess the efficacy of tofacitinib in patients with chronic pouchitis.

Hypothesis: Tofacitinib is effective in reducing clinical symptoms (modified pouchitis disease activity index), inflammatory biomarkers (fecal calprotectin), and endoscopic appearance among patients with chronic pouchitis.

Objective 2: Assess the safety of tofacitinib in patients with chronic pouchitis

Hypothesis: Tofacitinib is safe and well tolerated in patients with chronic pouchitis

Objective 3: Determine the effect of oral tofacitinib on health-related quality of life in patients with chronic pouchitis.

[figure not shown]
Hypothesis: Tofacitinib treatment is associated with improved HRQOL in patients with chronic pouchitis

Study Design and Methods

Overview of Study Design

The proposed study is a phase 2, open-label study of tofakinib in treatment of patients with chronic pouchitis. Patients with chronic active pouchitis will be recruited from the Cedars-Sinai Inflammatory Bowel Disease Center. The total expected duration of participation is 16 weeks including a 4-week screening period, 8 weeks of tofakinib therapy and an end of study visit 4 weeks after completion of 8-week tofakinib treatment. Subjects experiencing early withdrawal from study will be scheduled for a safety follow-up visit 4 weeks after the date of withdrawal. The primary outcome is a reduction in the mPDAI score ≥ 2 at week 8 compared to baseline. We will also assess secondary outcomes including changes in clinical symptoms, fecal calprotectin, HRQOL, and mucosal appearance.

Figure 1: Study Design

Study Population

The study will be open to adult patients (ages 18-80 years) seen at the Cedars-Sinai Inflammatory Bowel Disease Center who meet eligibility criteria.

Inclusion criteria

1. Male or female subjects ages 18 to 80

2. Subjects with a history of proctocolectomy with ileal pouch anal anastomosis (IPAA) for UC at least 6 months prior to screening.
3. Subjects with pouchitis that is chronic, defined by a mPDAI score ≥ 5 assessed as the average from 3 days immediately prior to the baseline study visit and a minimum endoscopic subscore of 2 (outside the staple or suture line) with either (a) ≥ 3 recurrent episodes within 1 year prior to the screening treated with ≥ 2 weeks of antibiotic or other prescription therapy, (b) requiring maintenance antibiotic therapy taken continuously for ≥ 4 weeks immediately prior to the baseline study visit, or (c) not responding to $>= 4$ weeks of antibiotic therapy.
4. Women of childbearing potential must have documentation of a negative pregnancy test at screening and must agree to use two highly effective methods of birth control during the study and for at least 1 month after completion of study drug dosing.
5. Subjects willing and able to give informed consent.

Exclusion criteria

1. Subjects with IPAA surgery done for Crohn's disease (CD) or familial adenomatous polyposis (FAP) indications.
2. Subjects with CD-like complications including non-anastomotic strictures and active perianal fistulae, isolated or predominant cuffitis or mechanical complications of the ileal pouch.
3. Surgical complications such as anal stenosis, anastomotic leak, or fistula.
4. Subjects with prior exposure to tofacitinib.
5. Subjects with impending need for surgery.
6. Subjects with a diverting stoma.
7. Subjects with a prior history or risk factors for venous thromboembolism.
8. Subjects with active bacterial, parasitic, fungal, mycobacterial, or viral infection (including *C. difficile* and GI infections observed upon stool testing at screening), any infection requiring hospitalization or intravenous antibiotics within 3 months prior to screening, any infection requiring oral antimicrobial treatment within 2 weeks prior to screening.
9. Subjects with a history of latent or active tuberculosis or a positive QuantiFERON[®]-TB Gold result.
10. Subjects positive for hepatitis B virus (HBV) surface antigen, hepatitis B virus core antibody with a negative hepatitis B surface antibody or with detectable serum hepatitis B DNA.
11. Female subjects who are pregnant, lactating, breastfeeding or planning to become pregnant during the study or within 1 month after the last dose of study drug.
12. Female subjects of childbearing potential who are sexually active with non-sterilized male partners and do not agree to using two highly effective methods of contraception from signing of informed consent throughout the duration of the study and for 4 weeks after the last dose.
13. Subjects with clinically significant laboratory abnormalities at study screening including: AST or ALT $\geq 3x$ the upper limit of normal, alkaline phosphatase $\geq 2x$ the upper limit of normal,

total bilirubin \geq 2 mg/dL (unless confirmed diagnosis of Gilbert's), estimated creatinine clearance $<$ 60 mL/min, total white blood cell count (WBC) $<$ 3 \times 10⁹/L, absolute neutrophil count $<$ 1.3 \times 10⁹/L, absolute lymphocyte count $<$ 0.5 \times 10⁹/L, hemoglobin $<$ 8 g/dL, or platelet count $<$ 100 \times 10⁹/L.

14. Subjects with evidence of active or history of clinically significant endocrine, pulmonary, cardiovascular (including uncontrolled hyperlipidemia [defined as LDL $>$ 200 mg/dL, total cholesterol $>$ 300 mg/dL, triglyceride $>$ 500 mg/dL]), hepatic, GI, psychiatric, oncologic or neurological disease as determined by the investigator at screening.
15. Subjects with an active solid organ or hematological malignancy (except non-melanoma skin cancers), or a history of a solid organ or hematological malignancy within the last 5 years.
16. Subjects with an organ transplant.
17. Subjects who received a live vaccine within 4 weeks of screening visit.
18. Subjects with condition(s) that in the opinion of the study investigators, may interfere with the participants ability to comply with the study procedures.

Concomitant medications

Study subjects will be allowed to remain on permitted concomitant medications provided the patient is on a stable dose for \geq 2 weeks prior to starting tofacitinib. Patient will need to stay on stable doses of these medications for the study duration of 8 weeks.

1. Antibiotics
2. Antidiarrheal agents
3. Oral corticosteroids including budesonide, up to doses of prednisone 20mg daily (or equivalent), or budesonide 9mg daily.
4. Probiotics

The following medications will not be allowed during the study:

1. Azathioprine, 6-mercaptopurine, or methotrexate within the 28 days prior to dosing visit.
2. Adalimumab, infliximab, golimumab, etanercept, certolizumab or vedolizumab within the 60 days prior to the first study visit or with negative drug concentration
3. Ustekinumab within 120 days prior to the first dosing visit or with negative drug concentration.
4. Intravenous corticosteroids within the 14 days prior to the first dosing visit.
5. Topical mesalamine or topical steroid within the 14 days prior to the first dosing visit.
6. Mycophenolic acid, tacrolimus, or cyclosporine within 60 days prior to the first dosing visit.

Treatment with Tofacitinib

Eligible subjects will be given tofacitinib 10mg twice daily for an 8-week duration. Study drug will be supplied for 4 weeks each at the baseline and week 4 visits.

Study Visits and Procedures

There are 5 study visits and 2 pouch endoscopic procedures during this 12-week study.

Screening Period (Week -4 to Day 0)

After giving informed consent, subjects will undergo up to a 4-week screening period to provide baseline data and be assessed for eligibility. The subjects will have a screening visit during which they will undergo an assessment of their medical history, symptom assessment and a complete physical examination with vital signs, height and weight measurement. They will also undergo complete blood count with automated differential, serum chemistries, serum C-reactive protein (CRP), lipid panel, QuantiFERON®-TB Gold test, urinalysis, fecal calprotectin, infectious stool studies, electrocardiogram (ECG), and chest X-ray. Subjects who satisfy the inclusion criteria and do not meet any exclusion criteria will proceed with pouch endoscopy with biopsies to confirm endoscopic eligibility and assess a baseline mPDAI endoscopic subscore. The pouch endoscopy will be scored by a central reader to reduce the risk of bias. If the subject meets all the eligibility criteria, he/she may be enrolled into the study. The subjects will be required to maintain a daily paper-based symptom diary starting immediately after the screening visit, although only symptoms during the 3 days preceding the study visits will be used for the calculation of the mPDAI score for the appropriate study visits.

Baseline Visit (Week 0)

At the baseline visit, subjects' eligibility for the study will be confirmed. Vital signs will be recorded, and a targeted physical examination will be performed. The symptom diary will be reviewed for calculation of the mPDAI score, and subjects will complete the CGQL questionnaire. At the end of the visit, the subjects will be given a 4-week supply of tofacitinib to be taken at a dose of 10 mg twice daily.

Week 4 and Week 8 Visit (± 3 days)

At the week 4 and week 8 visit, the subjects will undergo assessment for concomitant medication use, adverse effects and compliance with the study drug. Physical assessment will include vital signs and a symptom driven targeted physical examination. Blood, urine and stool will be collected for hematology, chemistry, CRP, urinalysis and fecal calprotectin measurement. Symptom diary will be reviewed, and subjects will complete the CGQL questionnaire. At the end of week 4 visit, the second 4-week supply of the study drug will be dispensed to the subjects. At the end of 8 weeks, the subjects will stop taking the study drug and undergo a pouch endoscopy with biopsies for calculation of mPDAI score to assess treatment response. The pouch endoscopy will be scored by a central reader to reduce the risk of bias.

Week 12 (± 3 days) or Early Termination Visit

The week 12 visit will be the final visit. Subjects who are withdrawn earlier from the study (per study rules and subjects who withdraw consent) after receiving study medication will complete

an early termination visit. At this visit, subjects will undergo a physical assessment, review of medications, adverse event assessment and blood, urine and stool collection for hematology, chemistry, CRP, urinalysis and fecal calprotectin measurement. Symptom assessment and CGQL questionnaire completion will also be performed.

Table 1 - Schedule of Study Procedures and Visits

Study visit	Screening (Week -4 to day 0)	Baseline (Day 1)	Week 4	Week 8	Week 12
General					
Informed consent	x				
Medication/Medical History	x				
Smoking Status	x				
Height, weight, BMI	x	x	x	x	x
Vital Signs	x	x	x	x	x
12-lead ECG	x				
Physical Examination	x	x	x	x	x
Chest X-ray	x				
Tuberculosis and HBV testing	x				
Study Drug Dispensing		x	x		
Clinical, laboratory, endoscopic and safety assessments					
Pregnancy Test (females only)	x				
Urine pregnancy test		x	x		
Chemistry, Hematology, Urinalysis	x		x	x	x
Stool C. difficile test	x				
Fasting Lipid Panel	x		x	x	x
C-Reactive Protein	x		x	x	x
Pouch endoscopy and biopsies	x			x	
Fecal calprotectin	x		x	x	x
Symptom Assessments	x	x	x	x	x
Concomitant medications	x	x	x	x	x
mPDAI		x		x	
Adverse event assessment			x	x	x
CGQL		x	x	x	x

Evaluation and Outcomes

The primary outcome of the study is clinical response at 8 weeks (defined below) as a measure of treatment efficacy. Other efficacy endpoints will include individual clinical, biochemical, and endoscopic assessments. Key secondary outcomes include assessment for safety and health-related quality of life.

Primary Endpoint

1. Proportion of subjects with clinical response defined as reduction in mPDAI score ≥ 2 from baseline at 8 weeks.

Secondary Endpoints

1. The proportion of subjects with clinical response, defined as an mPDAI score of ≥ 5 at 8 weeks with ≥ 2 -point decrease from the baseline score at 8 weeks.
2. The proportion of subjects with clinical remission at 8 weeks, defined as mPDAI score of < 5 with a ≥ 2 -point decrease from the baseline mPDAI score.
3. Change in mPDAI score at 8 weeks compared to baseline.
4. Change in mPDAI clinical sub-score at week 4 and week 8 compared to baseline.
5. Change in mPDAI endoscopic sub-score at week 8 compared to baseline.
6. Change in IBD-related quality of life as measured by Cleveland Global Quality of Life (CGQL) at week 4 and week 8 compared to baseline.
7. Safety, as determined by incidence of treatment-emergent adverse events. Adverse events of interest will include thromboembolic events and herpes zoster.

Efficacy Assessments

Efficacy measurement

The following will be used for definitions of clinical, biochemical, and endoscopic efficacy:

1. Clinical response defined as an mPDAI score of ≥ 5 at 8 weeks with a 2-point decrease from the baseline mPDAI score.
2. Clinical remission defined as mPDAI score < 5 after 8 weeks of treatment.
3. Change in mPDAI score from baseline to week 8.
4. Change in clinical and endoscopic mPDAI sub-scores from baseline to week 8.
5. Change in fecal calprotectin from baseline to week 8.
6. Change in serum C-reactive protein from baseline to week 8.

Symptom Diary

The subjects will be required to maintain a paper-based symptom diary to be completed daily starting after the initial screening visit. The symptoms recorded will include frequency of bowel movements, fecal urgency, abdominal pain/cramps, fever and blood in stools. The symptoms during the 3 days preceding the study visits will be used for the calculation of the mPDAI score for each study visits.

Pouch disease activity

Pouch disease activity assessment will be done using mPDAI, which is a combination of 6-point clinical and 6-point endoscopic scores. It has been shown to have excellent accuracy for pouchitis disease activity assessment with an area under the receiver operative characteristic curve of 0.995 and a sensitivity and specificity of 97% and 100%, respectively, compared to the pouch disease activity (PDAI) score, which is more complex as it includes histological activity

score in addition to clinical and endoscopic scores¹⁷. mPDAI score will be calculated at each study visit.

[Health-related quality of life](#)

Health related quality of life will be measured using the validated CGQL. The CGQL is a 3-question patient-reported assessment, which asks to rate the following questions on a 0-10 scale, with 0 being worst and 10 being best:

1. Current Quality of Life?
2. Current Quality of Health?
3. Current Energy Level?

Patients will be asked to complete the CGQL questionnaire at each study visit.

[Laboratory markers](#)

Serum CRP and fecal calprotectin will be used as laboratory markers of pouchitis activity. These will be assessed during the screening period and at week 4, 8 and 12 visits.

[Safety Assessment](#)

Subject safety will be assessed on all study visits using standard measures, including vital signs, symptom history, concomitant medication usage history, physical examinations, and blood and urine laboratory tests. Specifically, subjects will be assessed for the known potential adverse events to tofacitinib including anemia, peripheral cytopenias, lipid panel derangements, elevation of liver aminotransferases, thromboembolic events and infections.

[Statistical Methods](#)

[Sample Size Estimation](#)

Since this is a pilot study, no sample statistical sample size estimation was performed.

[Data Analysis](#)

Study subject demographics (age, gender, race), baseline characteristics (height, weight, and BMI), IBD history, prior IBD-related medication use, concomitant medications and baseline laboratory tests will be reported using descriptive statistics. All subjects in the study who received at least one dose of the study drug will be included for analysis. Missing data or early termination will be handled by non-responder imputation. Remission and response rate will be assessed using descriptive statistics. Change in mPDAI, CGQL scores, serum CRP and fecal calprotectin compared to baseline will be assessed using Wilcoxon signed-rank test. Adverse events will also be reported using descriptive statistics. Data will be considered significant at the two-sided p value of <0.05 where applicable.

Publication Plan

After the completion of the study and analysis of the data, we will submit the results of this study to national gastroenterology meetings (ie. Digestive Disease Week or American College of Gastroenterology Annual Meeting) followed by manuscript submission for publication in a high impact peer-reviewed journal.

Anticipated Project Timeline

Based on the clinical volume at Cedars-Sinai Medical Center, we anticipate enrolling 12 subjects in this research study over a period of 28 months. Last patient study visit will be 12 weeks later. This will be followed by data analysis and writeup/submission of study abstract and manuscript.

Task	Month											
	1-2	3-4	5-6	7-10	11-14	15-18	19-22	23-26	27-30	31-34	35-36	37-39
Obtain IRB approval												
Enrollment												
Final study visit												
Data analysis												
Prepare / submit abstract												
Prepare / submit manuscript												

References

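### The 2-week stable-dose rule counts back from the first tofacitinib dose, while the baseline endoscopic subscore may be up to 4 weeks old, so a permitted drug begun in between could contribute to response (minor)

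*Combined protocol and SAP*

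**What the plan says.** All references are to the combined protocol and SAP.

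- **Concomitant medications.** The rule opens "Study subjects will be allowed to remain on permitted concomitant medications provided the patient is on a stable dose for" and sets the period at no less than "2 weeks prior to starting tofacitinib. Patient will need to stay on stable doses of these medications for the study duration of 8 weeks". The permitted list includes antibiotics and oral corticosteroids. Among the disallowed items is "Topical mesalamine or topical steroid within the 14 days prior to the first dosing visit"; intravenous corticosteroids carry the same 14-day limit.
- **Screening Period.** "After giving informed consent, subjects will undergo up to a 4-week screening period". On the order of events: "Subjects who satisfy the inclusion criteria and do not meet any exclusion criteria will proceed with pouch endoscopy". That endoscopy supplies the baseline endoscopic subscore. No maximum interval from it to the first dose is given.
- **Overview of Study Design.** "The total expected duration of participation is 16 weeks including a 4-week screening period".
- **Table 1.** Pouch endoscopy is marked at screening and week 8 only. CRP and fecal calprotectin are marked at screening and not at baseline. Concomitant medications are reviewed at all five visits.
- **Clinical half of the score.** "only symptoms during the 3 days preceding the study visits will be used for the calculation of the mPDAI score". Inclusion criterion 3 requires pouchitis "defined by a mPDAI score ≥ 5 assessed as the average from 3 days immediately prior to the baseline study visit".
- **Primary Endpoint and Data Analysis.** Response is a fall of at least 2 mPDAI points from baseline at week 8, summarised descriptively in a single-arm study.

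**The concern.** Two time points that ought to coincide do not. Stability is counted back from the first dose, whereas half of the baseline score is fixed at an endoscopy that can be earlier than the start of the stability window. A subject scoped on day -25 who begins an oral corticosteroid on day -20 meets the rule as written. The baseline endoscopic subscore then predates both that drug and tofacitinib, and the week-8 endoscopy follows both.

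A 2-point fall can come from the endoscopic half alone. With no control arm, and no planned analysis that identifies such subjects, a response of this kind would be credited to tofacitinib.

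**Working it through.** The plan has no sample-size or power figure to reproduce; it states that none was calculated. The check is therefore date arithmetic. The first dose is day 0.

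**Inputs.** Stability window 14 days (Concomitant medications). Screening up to 28 days (Screening Period). mPDAI of 6 clinical plus 6 endoscopic points (Pouch disease activity). Entry total at least 5 with an endoscopic subscore of at least 2 (Inclusion criteria). 12 subjects anticipated (Anticipated Project Timeline).

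**1. Window in which a start after the endoscopy still complies.** With D the days from endoscopy to first dose, G = max(0, D - 14).

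| D (days) | G (days) |
|---|---|
| 28 | 14 |
| 25 | 11 |
| 21 | 7 |
| 18 | 4 |
| 14 or fewer | 0 |

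The endoscopy follows the other eligibility checks. If all 28 days are used and those checks take w days (an assumption), D = 28 - w, so w = 3, 7, 10 or 14 gives G = 11, 7, 4 or 0. The 14-day value is a limit, not an expectation.

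**2. Does other text close the window?** Exclusion 8 concerns antimicrobials for infection before screening. Entry route (b) requires at least 4 weeks of continuous antibiotics before baseline, and route (c) failure of at least 4 weeks of antibiotics. Both narrow new antibiotic starts for subjects entering that way. Route (a) does not, and no route limits corticosteroid starts or increases.

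**3. G is not a measure of bias.** Take a drug started on day -14, the latest compliant day, and a week-8 endoscopy on day 56, which is 14 + 56 = 70 days of exposure. A baseline endoscopy on day -13 has 1 day of exposure before it and 69 after. One on day -3 has 11 before and 59 after. G is 0 in both cases. A late endoscopy therefore removes only part of the problem.

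**4. The clinical half pulls the other way.** On diary days -3, -2 and -1 that same drug has been taken for 11, 12 and 13 days. Any early benefit lowers the baseline clinical subscore and leaves less room to fall. To keep a total of at least 5, an endoscopic subscore E needs a clinical subscore of at least max(0, 5 - E): E = 2 needs 3, E = 3 needs 2, E = 4 needs 1, and E = 5 or 6 needs none. A drug that works early can thus cost the subject eligibility.

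**5. Ceiling on the effect.** One misattributed responder is 1/12 = 8.3 percentage points; two are 2/12 = 16.7. For scale, 6/12 is 50.0% (exact 95% CI 21.1 to 78.9) and 5/12 is 41.7% (15.2 to 72.3).

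**6. CRP and calprotectin.** They are listed with the screening-visit tests, ahead of the endoscopy, and not repeated at baseline. Their uncovered interval is normally at least as long as that of the endoscopy. They are not part of mPDAI, so only their own change-from-baseline tests are affected.

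**The case against.** The strongest reply is that the rule lets subjects stay on existing treatment and nowhere invites a new start during screening. On that reading the sections do not contradict each other; a contingency has simply not been addressed. This has some force, and it makes such starts less likely. But the only time condition is the 2 weeks before tofacitinib, and a drug begun on day -20 satisfies it.

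It can also be said that endoscopy comes after the other checks, and that the 4 weeks is a maximum in one section and part of an expected total in another. That stands: the usual window is probably well under 14 days and may be nil.

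A reader might infer that the response rate will be inflated. The documents do not support that. They give no frequency of such starts, and the net direction is open. The clinical half is scored just before baseline. Topical therapy or intravenous corticosteroid need stop only 14 days before dosing, so it may still be in use at the baseline endoscopy, and its withdrawal works against response.

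A reader might also size the bias from the introduction's statement that budesonide is effective in 58-75% of patients. That effect is not defined as a 2-point mPDAI fall, so it shows that a permitted drug can be active and nothing about magnitude.

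**Conclusion.** The point holds as a minor one, with medium confidence. Followed exactly, the stability rule allows a permitted antibiotic or oral corticosteroid to be started or increased after the baseline endoscopy whenever that endoscopy is more than 14 days before dosing. Its endoscopic effect could then count towards the primary endpoint.

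The ceiling is 8.3 points per affected subject among 12, small beside the sampling error of a rate from so few. How many subjects would be affected cannot be derived from the documents, and the answer may be none. The conclusion assumes that the stability rule means what it says and that screening can run to its stated length. It does not show that bias has occurred or which way the net effect would run, and the length of the gap should not be read as the size of the bias.

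**What to change.** None of the following changes the permitted drugs or doses.

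1. Reconcile the stability window in Concomitant medications with the timing of the baseline endoscopy in Screening Period and Table 1, so that both refer to the same point. Scheduling the endoscopy late in screening helps only in part (step 3 of the working). State the related limitation for the screening CRP and calprotectin samples.
2. Record start, stop and change dates for concomitant drugs. Table 1 already has the review at every visit but does not say that dates are captured. Prespecify a sensitivity analysis of the primary endpoint that counts as non-responders the subjects whose antibiotic or corticosteroid was started or increased after the baseline endoscopy. Show separately a second, more conservative version that also includes starts or increases in the 2 weeks before it. That version can fail subjects whose new drug had already acted by the time of scoring, so it should not stand alone.
3. Report the endoscopy-to-dosing interval, and the numbers of starts, increases, stops and reductions, including topical or intravenous therapy stopped after the endoscopy.

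The cost is small: slightly less freedom in scheduling the endoscopy and its central reading, which could occasionally delay an enrolment; the added date recording; and one small extra analysis shown in two versions. No visit, sample or endoscopy is added.

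### The biologic washout rule in items 2 and 3 is inverted: as written, a negative drug level is a reason to bar a subject

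*Combined protocol and SAP*

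**What the plan says.** The section on concomitant medications ends with a six-item list introduced by "The following medications will not be allowed during the study". Two of the six items carry a clause about drug concentration:

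- Item 2, on five named anti-TNF agents and vedolizumab: use "within the 60 days prior to the first study visit or with negative drug concentration".
- Item 3: "Ustekinumab within 120 days prior to the first dosing visit or with negative drug concentration".

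Items 1, 4, 5 and 6 give a time window only; item 6, for example, reads "Mycophenolic acid, tacrolimus, or cyclosporine within 60 days prior to the first dosing visit". The numbered inclusion and exclusion criteria contain no biologic washout, so items 2 and 3 are the only rule that staff have on this point.

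**The concern.** A washout keeps residual drug out of the treatment period, and a negative concentration is evidence that it has succeeded. In items 2 and 3 the negative result is joined by *or* to a window that bars, under a heading that prohibits, so it becomes another reason to bar. Among subjects past the window who have a level, the text admits those with measurable biologic and turns away those without.

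Two errors are possible. A suitable subject may be refused because the drug is gone. If the sponsor wanted any measurable biologic to bar entry, a subject who still carries it may be admitted. The background section describes anti-TNF agents as widely used in chronic pouchitis and also mentions vedolizumab and ustekinumab, so prior exposure is foreseeable. The study is open-label with no control arm described, and the project timeline anticipates 12 subjects. Residual biologic effect in an admitted subject could not be separated from the effect of tofacitinib.

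**Working it through.** The plan states no figure that bears on this point, so there is nothing numerical to reproduce. The check is a reading of the rule and a comparison of its outcomes.

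**Does other text settle the meaning?** No.

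- The four items with only a time window read correctly under the heading, so the fault lies in the added clause.
- The screening procedures list "serum chemistries, serum C-reactive protein (CRP), lipid panel, QuantiFERON®-TB Gold test, urinalysis, fecal calprotectin, infectious stool studies, electrocardiogram (ECG), and chest X-ray", along with a blood count. No biologic level is named there or in Table 1, and neither place explains the clause.
- The exclusion criteria show two forms that work. Criterion 10 bars on a positive finding ("or with detectable serum hepatitis B DNA"). Criterion 13 writes an exception to a bar ("unless confirmed diagnosis of Gilbert", for the bilirubin limit). Items 2 and 3 follow neither form.

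**Rules compared.** Inside means that the last use falls within the item's window (60 days for item 2, 120 days for item 3).

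- Literal (L): barred if inside OR level negative.
- Repair A, negative level as an exception: barred if inside AND level not negative.
- Repair B, measurable drug as a second bar: barred if inside OR level measurable.

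| Case | L | A | B |
|---|---|---|---|
| Inside, negative | barred | admitted | barred |
| Inside, measurable | barred | barred | barred |
| Outside, negative | barred | admitted | admitted |
| Outside, measurable | admitted | admitted | barred |

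**Counts of cases.**

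- L against A: 2 of 4 differ (inside with negative level, outside with negative level). L wrongly bars both.
- L against B: 2 of 4 differ. L wrongly bars outside with negative level and wrongly admits outside with measurable level.
- L wrong whichever repair is meant: 1 of 4 (outside with negative level).
- L wrong under at least one repair: 3 of 4.
- A against B: 2 of 4 differ (inside with negative level, outside with measurable level), so the choice between them matters.

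Without a level, L, A and B agree: inside is barred and outside is admitted. The table is the same for items 2 and 3; only the window length changes.

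**The case against.** The strongest reply is that nobody would apply the text literally. Every item in the list gives a pre-study window, so the washout purpose is plain, and staff at a single specialist centre would probably take the clause as shorthand for a completed window or a negative level. The clause would also seldom come into play: no level is scheduled, so any result would come from outside the protocol, most plausibly ordered to show clearance. Under repair A the word *negative* is right and only the connecting word is wrong. The four-case counts describe logical cells, not subjects.

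All of this is fair as to weight. It does not rescue the wording. A reader who sees that the text fails must still choose between A and B, and these give opposite answers in two cases, so two members of staff could decide differently about the same patient.

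A stricter third rule, requiring both a completed window and a negative level, also cannot be excluded. It matches B wherever a level exists and differs only for a subject outside the window with no level, whom it would bar. That is a further reason to have the sponsor state the rule.

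It can also be said that the list governs medications and is not one of the numbered exclusion criteria. But its windows run before dosing and can only work as entry conditions.

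**Conclusion.** The concern holds. Items 2 and 3, followed as written, give the wrong decision for a subject past the window with a negative level under either repair. They also give the wrong decision in one further case under each repair. Repair A is the likelier intent, but the document does not establish it.

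The severity is minor. The clause affects only subjects for whom a drug level exists, and the document does not say how many that would be, so no number of subjects is claimed. The protocol reports that no sample size estimation was done, and no endpoint, threshold or error rate depends on this clause. The conclusion assumes only that the heading means what it says and that a negative concentration means no measurable drug.

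**What to change.** The sponsor should state which rule is meant and reword both items, leaving each item's window and its starting point unchanged.

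- Default (repair A): in items 2 and 3, replace the final clause with *unless a negative (undetectable) drug concentration is documented*.
- Alternative (repair B), if measurable drug is meant to bar entry whatever the time since last use: replace it with *or with a detectable drug concentration*.

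The cost is a two-line wording edit. Under the alternative, the sponsor should note that no drug-level assay is currently scheduled, so the bar could be applied only to subjects who happen to have a result.
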